9.4.3 Risks Associated with Spirometry

Spirometry is a very low-risk procedure with few side effects. Participants may experience transient coughing, lightheadedness, dizziness, fainting (more commonly in older persons with impaired lung function), and chest tightness. These symptoms usually resolve after the test is complete.

To minimize risks associated with this procedure, very conservative exclusions for undergoing spirometry will be implemented, testing is done in a seated position, and study personnel will be trained to look for signs of dizziness or other problems and will stop the maneuver if necessary.

Any risk of transmitting infection from one participant to the next through the use of shared equipment is minimized by using disposable nose clips, spacers, and

mouthpieces (spirettes), which have the additional protection of a built-in bacterial filter.

9.4.4 Risks Associated with Venipuncture

Peripheral blood sampling entails a risk of mild discomfort, bleeding, bruising, with infrequent hematoma formation, vein irritation, or infection from the venipuncture, and a possibility of lightheadedness or fainting.

To minimize risks associated with this procedure, the amount of blood drawn will be limited to no more than 100 mL, study staff who are appropriately trained in phlebotomy will perform this procedure, and attempts to draw blood will be limited to up to three attempts if the participant agrees.

9.4.5 Risks Associated with Collection of Nail Clippings, Hair, Saliva, and Buccal Cells

Collection of nail clippings, hair, saliva, and buccal cells are all very low-risk procedures with few side effects. Participants may rarely experience mild local trauma or infection at the collection site.

Although no specific genetics research is planned under this protocol, if DNA is isolated from these samples by future researchers for genetic analyses, the risks associated with genetics research may apply. This includes breach of confidentiality of test results that could result in impacts on employability, insurability, discrimination, or psychosocial risks to the participant or participant's family.

9.4.6 Risks Associated with Questionnaire Administration

The questionnaires used for this study are based on instruments that are widely used in epidemiological studies and disaster research and have been evaluated for their reliability, validity, ease of use and overall low participant burden. All mental health questions included in the core questionnaires listed in Appendix C have been previously reviewed and approved by the NIEHS IRB for use in other studies.

The main risk in questionnaire administration involves discomfort around sensitive health topics or personal experiences that may be traumatic; in some cases such questions could trigger emotions, stress, or other reactions that are difficult or painful for the participant to experience (e.g., post-traumatic stress disorder). To help minimize this risk, participants will be told that they may skip any or all questions or end the interview at any time. Also, to the extent possible at the study site, a private setting for completing sensitive surveys or interviews will be provided. Further, field staff receive training in handling emotionally difficult situations and have a list of mental health referral sources available to participants in distress.

9.4.7 Other Risks, Loss of Privacy, and Breach of Confidentiality

No risks are anticipated for other study procedures, with the exception of the potential for loss of privacy or breach of confidentiality as a result of inadvertent disclosure of information collected for research purposes (e.g., de-identified data distributed through controlled-access procedures could be linked back to a participant in ways that cannot be foreseen at present). To help minimize the risk of forced disclosure of information that could identify a participant, the study team will obtain a Certificate of Confidentiality (see [Section 9.5.1](#)).

Participants will be informed about the possibility for loss of privacy or breach of confidentiality. We will not collect information about the participant's employer. Participants will be informed that since employer information will not be collected, the study team cannot share their personal study information with their employer. However, there may still be some risk of adverse outcomes should any results of tests or procedures that indicate physical or mental health problems be inadvertently acquired by a participant's employer.

Measures to protect privacy and confidentiality are further described in [Section 9.5](#).

Participants will be informed of any health information learned in course of conducting study procedures indicative of an immediate risk to the health or safety of the participant (e.g., extremely high blood pressure or resting heart rate in a deployed worker engaged in strenuous physical activity).

Finally, if any procedures or evaluations are added to this protocol per [Section 6](#), they will be listed and their risks described in Appendix B: Protocol Amendment Checklist.

9.5 Protection of Participants' Privacy and Confidentiality

The PI is responsible for ensuring that the participants' privacy and confidentiality is maintained. All records will be kept confidential to the extent provided by federal, state, and local law. Only study staff will have routine access to study records and data. In situations where data collection takes place in multiple sites, study staff will only have access to site-specific data (i.e., only central coordinating center staff will have full access to multi-site data). Research samples, electronic case report forms (eCRFs), and other research documents will be coded with a unique participant identification number and will not include personally identifiable information (PII) to the extent possible (e.g., some questionnaires may collect PII). The results of the study may be presented in reports, published in scientific journals, or presented at medical meetings. However, participants will not be identified in any study reports.

Study information will be kept secure and private in two locations as follows:

- Hard copies of the signed consent forms and any paper data collection tools will be kept in a locked study file cabinet

- Electronic records with personal identifying information, such as name, address and phone number and other data collected as part of the study procedures will be stored in a password-protected study management database

Clinical information will not be released without written permission of the participant, except as necessary for monitoring by the IRB, NIEHS, and Office of Human Research Protection (OHRP). The investigator will inform participants that study monitors and other representatives of the NIEHS may inspect research records. Participants will also be informed that study monitors and other NIEHS representatives are bound by agreement and the law to maintain participant privacy and confidentiality.

9.5.1 Certificate of Confidentiality

To help safeguard the privacy of human research participants enrolled in this study, the study team will obtain a Certificate of Confidentiality to protect against compulsory legal demands (e.g., a court subpoena, or any federal, state, or local civil, criminal, administrative, legislative, or other proceedings) for identifying information or identifying characteristics of any research participants.

9.6 Study Discontinuation

Participants may voluntarily withdraw from the study at any time. Participants will be informed that unless explicit written instructions are received, investigators will continue to use data and samples collected up to the point of withdrawal. Study staff will effectively destroy all known remaining samples by anonymizing the samples using a newly assigned ID number and report what was done to both the subject and to the IRB. This decision will not affect the subject's participation in this protocol or any other protocols at NIH. Anonymizing the samples will effectively terminate any association the samples have with the study participant, fulfilling their request, while simultaneously providing samples that can be used for laboratory QA/QC procedures. However, should the subject specifically request it in writing, we will physically destroy all remaining samples.

Study staff will seek feedback from the participant to determine reasons for discontinuation and to identify any barriers that can be addressed to keep the participant in the study. The reasons for all discontinuations will be recorded in the data collection system and routinely monitored by the investigator. Common barriers to ongoing participation may be addressed by changes in retention strategies or study design.

10 Data and Safety Monitoring Plan

The PI will be responsible for ensuring the safety of research subjects and the integrity of research data, consistent with regulatory and NIH requirements.

There is minimal risk associated with the study procedures and evaluations, and the main objective of this study is to create a repository of specimens and data.

Thus, the nature of this study does not warrant the use of a Data and Safety Monitoring Board (DSMB).

Prior to implementation of this study, the protocol, the proposed patient consent forms, and any other patient materials (additional materials are listed in Appendix A: List of Appendices) will be reviewed and approved by the NIEHS IRB, according to 45 CFR 46. After study implementation, the NIEHS IRB requires that the study team report back to the Board within 60 days of study initiation regarding any study activities that impact the safety of research subjects. A template for the Review of RAPIDD Protocol Implementation Report has been developed and is available in Appendix F. The NIEHS IRB must receive and approve this report in order for the RAPIDD study to continue enrolling new participants.

The NIEHS IRB will approve all amendments to the protocol or informed consent, and will conduct continuing annual reviews so long as the protocol is open to accrual or sample/data storage continues under this protocol.

10.1 Clinical Monitoring Plan

The coordinating center will designate an independent clinical monitor to carry out monitoring visits. The purpose of the visits is to ensure that the rights of human participants are protected, that the study is implemented in accordance with the protocol and NIEHS standards, and that the integrity of study samples and data are maintained. The monitor will review various aspects of the study including, but not limited to:

- Documentation of informed consent
- Compliance with the protocol
- Documentation and reporting of unanticipated problems, adverse events, and protocol deviations
- Handling and storage of biological specimens
- Completeness and accuracy of study data

The scheduling and frequency of monitoring visits will depend on the date the first participant is enrolled, the rate of enrollment, and the anticipated duration of operations at a given study site. The monitor, in conjunction with the coordinating center, will work with the site manager or investigator to schedule the visits at a time that is mutually agreeable. The monitor will document the date and time of all visits on a monitoring log that will be stored in the study regulatory binder.

During the visits, the site manager or investigator will provide the monitor with workspace and access to site facilities, source documents, and research records. The site manager or investigator will also be available to meet with the monitor to discuss findings and reply to inquiries.

After the visit, the monitor will produce a report to document all findings, discussions, and solutions. The report or a follow-up letter summarizing the contents of the report will be sent to the PI, the coordinating center, and the site manager. Additional follow-up may be conducted by email and telephone as needed.

10.2 Reporting of Unanticipated Problems, Adverse Events and Protocol Deviations

The PI will be responsible for ensuring that unanticipated problems (UPs), Adverse Events (AEs), and deviations are detected, documented, and reported in accordance with the protocol, NIEHS IRB policies, applicable SOPs (e.g., NIH HRPP SOP 16 “Reporting Requirements for Unanticipated Problems, Adverse Events and Protocol Deviations”), and federal regulations. Recording and reporting of Adverse Events are described below within Section 10.3.

Serious unanticipated problems and serious protocol deviations will be reported to the IRB and CD as soon as possible and in writing on the Problem Report Form not more than 7 days after the PI first learns of the event. Not serious unanticipated problems and not serious deviations will be reported to the IRB and CD as soon as possible and in writing on the Problem Report Form not more than 14 days after the PI first learns of the event.

Deaths will be reported to the Clinical Director within 7 days after the PI first learns of the event.

All adverse events, deviations, and unanticipated problems will be summarized and reported at the time of Continuing Review.

10.3 Adverse Events

Adverse events associated with the study procedures are expected to occur very infrequently. Most of the risks associated with study procedures are mild, causing only transient discomfort.

10.3.1 Definition of an Adverse Event (AE)

Generally, an AE is defined as any unanticipated or unintended medical occurrence or worsening of signs, symptoms, or disease that occurs in a study participant after the time informed consent is obtained, regardless of the causal relationship of the event to study procedures. For the purposes of this study, signs and symptoms of pre-existing conditions that occur during the study will not be recorded as AEs, unless they are exacerbated by study procedures (based on the investigator’s medical judgment). Additionally, medical events that occur outside the protocol-defined surveillance period (see Section 10.3.3) will not be recorded as AEs.

10.3.2 Definition of a Serious Adverse Event

A Serious Adverse Event (SAE) is defined as an AE occurring during the protocol-defined surveillance period (see Section 10.3.3) resulting in one of the following outcomes:

- Death
- Life-threatening event (defined as a condition that places a participant at immediate risk of death)
- In-patient hospitalization or prolongation of an existing hospitalization
- Persistent/significant disability or incapacity
- Medically important event that jeopardizes the participant and requires intervention to prevent one of the outcomes listed above

10.3.3 Adverse Event Surveillance Period

Surveillance for AEs will include the time period from when informed consent is obtained at the registry visit until completion of the visit. At the end of each visit, participants will be asked if they experienced any problems during the visit. Participants will also be instructed to contact the study staff if they experience any new problem within two days of a visit.

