10.3.4 Reporting of Adverse Events

Only clinically significant adverse events (based on the investigator's medical judgment) will be reported to the IRB. Examples of clinically significant adverse events include:

- Fainting during spirometry or blood collection
- Respiratory distress induced by spirometry that requires medical attention
- Prolonged bleeding, hematoma formation, or infection associated with blood collection that requires medical attention

Field staff will be trained to detect and respond to clinically significant adverse events, and will be expected to report clinically significant adverse events to the coordinating center immediately.

At the time of the continuing IRB review, the PI will provide an aggregate summary of all clinically significant AEs.

Given the minimal risk of the procedures contained in the protocol, we anticipate SAE's to be very infrequent and therefore should be reported regardless of cause or association with preexisting conditions. The PI will report SAEs to the NIEHS IRB and NIEHS Clinical Director as soon as possible, but not more than 7 days after the PI first learns of the event.

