10.3.5 Documenting Adverse Events

All AEs that are identified according to the definition provided in Section 10.3.1 will be entered onto a paper case report form (CRFs) or eCRFs, as applicable. The medical diagnosis of the event, time of onset, time of resolution or stabilization, the severity of the event, the investigator's judgment of the AE's relationship to the procedure, the expectedness of the event, action taken (if any), and outcome will also be recorded on the CRF. The CRF will be updated to reflect any changes in the status of the event that are recorded in source documents.

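### The only stated end of AE surveillance is the end of the visit, so procedure harms that begin later fall outside the AE and SAE record, in conflict with the plan's own two-day contact window and reportable examples

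*Protocol*

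**What the plan says.** Protocol Section 10.3.3 sets the period: "Surveillance for AEs will include the time period from when informed consent is obtained at the registry visit until completion of the visit". Participants are asked about problems at the end of each visit, and the section closes with a further instruction: "Participants will also be instructed to contact the study staff if they experience any new problem within two days of a visit".

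Three other subsections depend on that period:

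- Section 10.3.1 says that "medical events that occur outside the protocol-defined surveillance period (see Section 10.3.3) will not be recorded as AEs".
- Section 10.3.2 says that an SAE "is defined as an AE occurring during the protocol-defined surveillance period" and leads to one of the listed outcomes.
- Section 10.3.5 says: "All AEs that are identified according to the definition provided in Section 10.3.1 will be entered onto a paper case report form" (or its electronic equivalent).

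Section 10.3.4 gives examples of clinically significant AEs that go to the IRB. One of them is "Prolonged bleeding, hematoma formation, or infection associated with blood collection that requires medical attention". Section 9.4.4 names the same kind of harm as a known risk of the blood draw: "infrequent hematoma formation, vein irritation, or infection from the venipuncture".

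On periodic reporting, Section 10.2 says: "All adverse events, deviations, and unanticipated problems will be summarized and reported at the time of Continuing Review". Section 10.3.4 promises an aggregate summary of the clinically significant AEs only.

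**The concern.** The protocol sets up a way for participants to report problems after they leave and names post-draw complications as reportable. Its definitions then appear to leave no place to record such a report as an AE. No section says what staff should do with a two-day call once it is received.

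The AE counts have a use. Section 10 says there is no DSMB. It also says that the IRB must receive and approve the implementation report, due within 60 days, before enrollment of new participants can continue. Appendix F gives the purpose of that report as checking that the safeguards are adequate in the actual disaster setting, and its item V asks for a summary of adverse events. If the count leaves out harms with onset after the visit, the IRB sees an incomplete picture at the point where it decides on continuation. The Continuing Review summary has the same gap.

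**Working it through.** The protocol gives no figure to reproduce here. The check sets the sections side by side; the only arithmetic is the length of a visit.

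**1. How long the stated period lasts.** Inputs are the procedure times in Table 1 (Section 6).

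- Enhanced: 10 + 2 + 2 + 2 + 15 + 30 + 20 = 81 minutes.
- Basic: 10 + 2 + 2 + 2 + 15 + 10 = 41 minutes.
- Core: 10 + 5 + 5 = 20 minutes.

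These match the Table 1 totals. Surveillance starts once consent is obtained, so with the 10 consent minutes removed the period is about 71, 31 or 10 minutes. Table 2 shows no blood draw in the core set, so the post-draw examples concern the 41- and 81-minute visits. This assumes that the Table 1 times make up the whole visit.

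**2. The chain of rules.** The period ends at visit completion (10.3.3). An event outside it is not recorded as an AE (10.3.1). An SAE must be an AE that occurs in the period (10.3.2). CRF entry is prescribed for events that meet the 10.3.1 definition (10.3.5).

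**3. Applying the chain to four cases.**

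| Case | Literal result |
|---|---|
| Fainting during the draw or spirometry | AE, entered on the CRF |
| Complication that begins in the visit and leads to hospital admission next day | AE and SAE: Section 10.3.2 requires the event, not its outcome, to fall in the period, and Section 10.3.5 has the CRF updated as status changes |
| Infection, hematoma or bleeding from the draw with onset after the visit, reported the next day | Not an AE, not an SAE, no AE entry prescribed |
| The same, leading to hospital admission | Not an SAE, because the underlying event began outside the period |

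Only the last two rows are the problem. They are also the kind of event that the two-day instruction would bring in and that Section 10.3.4 lists as reportable. I assume, on general grounds and not from the protocol, that an infection from a blood draw would usually become apparent after a visit of this length.

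**4. What the other routes catch.** Section 10.2 sends unanticipated problems to the IRB and Clinical Director within 7 days if serious and 14 days if not, and deaths to the Clinical Director within 7 days. Neither route is tied to the surveillance period. Infection from venipuncture is a listed risk in Section 9.4.4, so it may not count as unanticipated. Neither route makes the event an AE in the counts.

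**5. Continuing Review.** Section 10.2 covers every AE, while Section 10.3.4 covers the clinically significant ones. The two differ for any AE judged not clinically significant.

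**The case against.** The strongest reply is that Section 10.3.3 says what surveillance will include, not what it is limited to. The two-day instruction stands in the same section, under the surveillance-period title, and Sections 10.3.1 and 10.3.2 point to that section as a whole. On this reading the two days are inside the period and the infection example fits. The authors may well have meant this. But visit completion is the only end point stated, and an exclusion rule needs a definite boundary. At best the text is ambiguous where staff must decide whether to complete a form.

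A reader might infer more than the text supports:

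- *That any hospital admission the day after a visit is outside the SAE definition.* It is not, if the event began during the visit.
- *That problems phoned in are thrown away.* No section says so. Section 10.3.6 requires evaluation, management and follow-up for any participant who reports an AE or SAE, and the Section 10.2 routes stay open. What is missing is a rule for recording the call.
- *That the share of harms missed can be read from the ratio of visit time to two days.* It cannot. Clock time is not event frequency, and two of the three examples in Section 10.3.4 (fainting, and respiratory distress induced by spirometry) belong to the procedures themselves.
- *That the protocol actively follows participants for two days.* Active questioning happens once, at the end of the visit; after that, reporting depends on the participant.

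On Continuing Review, Section 10.2 refers the reader to Section 10.3 for AE recording and reporting, so the specific section can be taken to govern. That mismatch is one of wording.

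It is also fair that this is a minimal-risk registry with no study treatment. The primary objective, the planned analyses and the sample size are untouched.

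**Conclusion.** The point holds as an internal conflict that needs reconciling. Read literally, Sections 10.3.1 to 10.3.3 and 10.3.5 keep procedure-related events with onset after the visit out of the AE and SAE record. The two-day instruction and the Section 10.3.4 examples show that the protocol expects to hear of such events and regards some of them as reportable. The consequence is an AE count in the 60-day report and at Continuing Review that omits those events, unless they enter as unanticipated problems or deaths under Section 10.2.

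The omission has a direction (undercounting) but no size that can be calculated, because the protocol gives no event rates. Sections 9.4.2 and 10.3 expect few and mostly mild events, so the absolute number is likely small. The conclusion rests on reading visit completion as the end of the period; on the looser reading, what remains is unclear wording. The matter is worth correcting before activation, but it does not threaten the study's scientific aims.

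**What to change.** State in Section 10.3.3 that the surveillance period runs from consent through the end of the two-day contact window that the section already contains. Align Sections 10.3.1, 10.3.2, 10.3.4 and 10.3.5 with that period, and add one sentence saying that problems reported in the window are entered on the AE CRF and assessed as AEs or SAEs. As a minor edit, make Sections 10.2 and 10.3.4 agree on whether all AEs or only clinically significant ones are summarized at Continuing Review.

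The cost is a short wording amendment and a CRF for each of the few participants who call. No procedure or visit is added. Two days will not capture every delayed infection. Nor need it cover nail clippings that Section 6.9 allows participants to collect themselves at a later time, although Section 9.4.5 gives that collection its own small risk. The text should say how a problem reported from later self-collection is to be recorded.
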